3.9 Liver event and laboratory trigger definitions

Table 3.7 Liver event and laboratory trigger definitions

	Definition/Threshold
LIVER LABORATORY TRIGGERS	
 • $3 \times \text{ULN} < \text{ALT/AST} \leq 5 \times \text{ULN}$. • $1.5 \times \text{ULN} < \text{TBL} \leq 2 \times \text{ULN}$.
LIVER EVENTS	
 • ALT or AST $> 5 \times \text{ULN}$. • ALP $> 2 \times \text{ULN}$ (in the absence of known bone pathology). • TBL $> 2 \times \text{ULN}$ (in the absence of known Gilbert's syndrome). • ALT or AST $> 3 \times \text{ULN}$ and INR > 1.5. • Potential Hy's Law cases (defined as ALT or AST $> 3 \times \text{ULN}$ and TBL $> 2 \times \text{ULN}$ [mainly conjugated fraction] without notable increase in ALP to $> 2 \times \text{ULN}$). • Any clinical event of jaundice (or equivalent term). • ALT or AST $> 3 \times \text{ULN}$ accompanied by (general) malaise, fatigue, abdominal pain, nausea, or vomiting, or rash with eosinophilia. • Any AE potentially indicative of a liver toxicity. *

AE: Adverse event. ULN: Upper limit of normal. ALT: Alanine aminotransferase. AST: Aspartate aminotransferase. ALP: Alkaline phosphatase. TBL: Total bilirubin. INR: International normalized ratio. *These events cover the following: Hepatic failure, fibrosis and cirrhosis, and other liver damage-related conditions; the non-infectious hepatitis; the benign, malignant and unspecified liver neoplasms.

3.10 Protocol deviations

The process by which reasons for exclusion are identified involves the creation of a protocol deviation edit specifications document, listing all potential deviations (identified programmatically using codes, per data collected). Using this list, potential deviations are identified by checking the data during the clinical conduct of the study. The identified potential deviations are then shared with the Novartis clinical team. The team meets to discuss the list on a monthly basis. Protocol deviations which can be identified programmatically will be done using validation procedures within OC/RDC. Once these discrepancies are confirmed to be protocol deviations, the system will automatically load these records into the DV (Protocol Deviations) domain. Potential protocol deviations identified manually will be proposed by the Study Lead (or Field Monitor) and cCRA and entered as discrepancies in the EDC database; based on the site's response, the Study Lead will confirm whether the protocol deviation is CSR reportable. These PDs will also be loaded into the DV domain by Novartis.

Once confirmed by the Novartis clinical team, the [REDACTED] biostatistics team will use the identified and confirmed list of protocol deviations from the DV domain as the potential reasons to exclude patients from the respective analysis set(s). Should the domain contain any of the below criteria, identified programmatically (by means of the codes which are assigned) the impact of the criteria will be considered major and summarized as such in the CSR.

Exceptions to the following inclusion/exclusion are considered as major protocol deviations and will lead to exclusion of patients from the relevant analysis sets:

Protocol Deviation Category: Selection criteria not met

Inclusion/Exclusion Criteria Number	Inclusion/Exclusion criteria text
Inclusion 1	Written informed consent must be obtained prior to any assessment is performed.
Inclusion 2	Patient must have had surgical fixation or arthroplasty of the hip fracture (Association for the Study of Internal Fixation [AO] Classification 31 A-C [AO Foundation 2013]) as confirmed by radiography.
Inclusion 3	Patient must be mentally competent, to have scored at least ≥ 21 on the Folstein Mini Mental State Examination (MMSE).
Exclusion 1	History of any other lower limb fracture in the past 6 months or any other major surgery to the lower limb in the past 3 months prior to randomization with persistent negative impact on lower extremity function.
Exclusion 2	Presence of isolated sub-trochanteric fractures (AO Classification 32 A-C, [AO Foundation 2013]).
Exclusion 3	History of refracture of the same hip. Only applicable to pre-amendment 2 patients.
Exclusion 4	Major mobility limitation (i.e. not able to walk 100 meters without stop and without help unilateral help being fine) in the past 3 months prior to hip fracture due to severe dyspnea, presence of permanent or progressive neurologic deficit (muscle weakness, spasticity, rigor or balance impairment), disabling joint or muscle pain in the hip or knee, intermittent claudication or major visual impairment.
Exclusion 5	Underlying muscle diseases, including history of or currently active form of inflammatory myopathies (i.e. dermatomyositis, polymyositis, etc.) or muscular dystrophies.
Exclusion 6	Neurological injury (e.g. stroke, cerebral palsy, spinal cord injury, muscular dystrophy, myasthenia gravis, etc.) or neurological disorders (e.g. Parkinson's disease, epilepsy, multiple sclerosis or diabetic polyneuropathy). Only applicable to pre-amendment 2 patients.
Exclusion 7	Subject was included despite known presence of medical conditions causing malabsorption of proteins (e.g. inflammatory bowel disease, celiac disease, short bowel syndrome, pancreas insufficiency). Only applicable to pre-amendment 2 patients.
Exclusion 8	Subject was included despite active gastrointestinal diseases/conditions known to cause malabsorption or increased enteric loss of proteins (e.g. inflammatory bowel disease, celiac disease, short bowel syndrome, pancreas insufficiency). Only applicable to subject randomized post

Inclusion/Exclusion Criteria Number	Inclusion/Exclusion criteria text
	protocol amendment 2.
Exclusion 9	Subject was included despite known heart failure with severity grade of NYHA Class III or IV.
Exclusion 10	Systemic use of vascular endothelial growth factor (VEGF) inhibitors within 6 months prior to randomization.
Exclusion 11	Use of any therapies known to affect muscle mass via modulation of androgen or growth hormone receptors or the synthesis of these hormones within 3 months prior to randomization or current use of high-dose selective beta2-adrenergic drug therapy.
Exclusion 12	Ongoing corticosteroid use or history of systemic corticosteroid use for at least 3 months (in the last year) prior to randomization at a daily dose greater than or equal to 10 milligram (mg) prednisone equivalent.
Exclusion 13	Currently enrolled in, or discontinued within the last 30 days (or 5 half-lives, or until PD effect is expected to return to Baseline, whichever is longer or longer if required by local regulations) from a clinical trial involving an investigational drug or off-label use of a drug, or are concurrently enrolled in any other type of medical research judged to be scientifically or medically incompatible with this study.

The following protocol deviations are considered as important and will lead to exclusion of patients from the analysis sets as decided by the Novartis clinical team during their monthly discussions:

Protocol Deviation Category	Protocol deviation description
Patient not withdrawn as per protocol	Patient not discontinued from treatment after informed consent withdrawn.
	Patient not discontinued from treatment after emergency/accidental unblinding.
	Patient not discontinued from study despite missing two infusions at any time during the treatment epoch.
Treatment deviation	Patient received study drug without being randomized into study.
	Patient randomized in error and study medication was given.
	Patient received wrong dose or strength of the study drug.
	Patient received expired study drug.
	Patient received wrong study medication (e.g. placebo instead of active drug).

Protocol Deviation Category	Protocol deviation description
Prohibited concomitant medication	Patient took a prohibited medication while in the study, however was not discontinued from the study.

The following protocol deviation terms (in the DV domain) will lead to the exclusion from the PP analysis set as decided by the Novartis clinical team:

Protocol deviation description
Mishandling of study drug medication at the site or by the patient (e.g. storage condition not respected) and patient took drug.
Subject received wrong dose or strength of the study drug

The final analysis set assignment [REDACTED] and identified major reason(s) for exclusion of patients, based on the confirmed list in the DV domain, from one or more of the analysis sets will be confirmed by Novartis prior to study unblinding at the time of the primary analysis. Following this, at the time of the primary analysis, routine study unblinding of the [REDACTED] biostatistics team may commence.

Treatment deviations (by identifying discrepancies between randomized treatment assignment and actual treatment received, using information in the DV domain and other domains provided by Novartis [randomization schedule and kit numbers]) and finalizing the [REDACTED] analysis set (with review by Novartis) will be determined after study unblinding of the treatment code and before the start of the primary analysis. Both treatment deviations and the [REDACTED] analysis set will be reviewed and confirmed by Novartis and an authorization form will be completed per [REDACTED] internal procedure. This information will be passed on to the medical writer to support development of the CSR.

Patients with treatment deviations, if identified, will be handled in the following way, in terms of the analyses:

- For Safety, patients will be analyzed per actual treatment received.
- For FAS, patients will be analyzed per randomized treatment assignment.
- For PP, they will be excluded.

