5.5.5 Permitted dose adjustments and interruptions of investigational treatment

Investigational treatment dose adjustments are not permitted.

Dose interruptions should be avoided for the duration of treatment. However for patients who are unable to tolerate the protocol-specified dosing scheme, dose interruptions of investigational treatment are permitted in order to keep the patient on study drug.

If a patient misses two doses, the subject must be discontinued from the investigational treatment (refer to [Section 5.5.9](#)).

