5.5.9 Discontinuation of investigational treatment or premature study discontinuation

Patients may voluntarily discontinue the investigational treatment for any reason at any time.

The investigator should discontinue investigational treatment for a given patient if, on balance, he/she believes that continuation would be detrimental to the patient's well-being.

Investigational treatment *must* be discontinued under the following circumstances:

- Use of prohibited treatment as per [Table 5-1](#).
- Any other protocol deviation that results in a significant risk to the patient's safety
- Breaking of the blind (inadvertently or for emergency reasons)
- Severe hypersensitivity reaction occurs
- Liver event definition met as per [Appendix 2](#)
- Deviations from the prescribed dose regimen for investigational treatment with 2 doses missed at any time
- Death
- Withdrawal of consent
- Sponsor decision to terminate (part of) the study

Investigational treatment *may* be discontinued under the following circumstances:

- Emergence of the adverse events that in the judgment of the investigator, taking into account the patient's overall status, prevent the patient from continuing participation in the study
- Any laboratory abnormalities that in the judgment of the investigator, taking into consideration the patient's overall status, prevents the patient from continuing participation in the study

At the time of protocol amendment #2 implementation, patients who have already received their Week 20 infusion of investigational treatment returned to the site at their next scheduled

visit and performed their End of Treatment visit. They continued as per the study visit schedule Table 6.1.

Patients who discontinue investigational treatment are NOT considered immediately withdrawn from the STUDY or to have withdrawn informed consent to participation (described in section 5.5.10). The patient must return approximately 28 days following the patient's last investigational treatment administration to complete the End of Treatment visit assessments (Table 6-1). If the patient was already off-treatment for a longer period, then the End of Treatment visit can be performed without delay. After completing the End of Treatment assessments, patients will enter a 4-week follow up and return for the End of Study visit. If the patient fails to return for these assessments for unknown reasons, every effort should be made to contact him/her as specified in Section 5.5.11.

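### Two exclusion terms in SAP 3.10 turn on leaving the study, whereas the protocol stops treatment only and keeps the patient for follow-up; the analysis sets affected are not named

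*SAP*

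**What the plan says.** **SAP 3.10** has a list of important deviations. Under the category for patients not withdrawn as the protocol requires, one term reads "Patient not discontinued from study despite missing two infusions at any time during the treatment epoch". The prohibited-medication term reads "Patient took a prohibited medication while in the study, however was not discontinued from the study". The sentence introducing the list says that these deviations "will lead to exclusion of patients from the analysis sets as decided by the Novartis clinical team during their monthly discussions". Another term in the same category as the first uses a different word: "Patient not discontinued from treatment after emergency/accidental unblinding".

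**Protocol 5.5.5** says "If a patient misses two doses, the subject must be discontinued from the investigational treatment". **Protocol 5.5.9** lists the circumstances in which investigational treatment must be stopped. They include "Deviations from the prescribed dose regimen for investigational treatment with 2 doses missed at any time" and "Use of prohibited treatment as per" Table 5-1. In Table 5-1 (section 5.5.8), the action shown against the drug classes, wherever one is legible, is to discontinue investigational treatment. Section 5.5.9 then adds: "Patients who discontinue investigational treatment are NOT considered immediately withdrawn from the STUDY". Such patients return about 28 days after the last dose for the end-of-treatment visit and, after a further 4 weeks, for the end-of-study visit. The footnote to Table 6-1 says the same.

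**SAP 2.4.1** recognises this group: its at-risk definition for follow-up counts patients who stop treatment early and go on into the planned 4-week follow-up.

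**The concern.** A patient who misses two infusions, stops treatment and attends both remaining visits has been managed as the protocol prescribes, yet meets the SAP term because that patient is still in the study. SAP 3.10 says that the criteria it lists will be considered major, and SAP 2.7 defines PP membership by the absence of major deviations. SAP 2.10 and 2.10.1.6 present the PP analysis as confirmation of the primary result. If the terms are applied as worded, the deviation table reports site handling errors that did not occur, and membership of the confirmatory set depends partly on whether the patient stayed in follow-up after the event. If missed infusions or prohibited-drug use differ between arms, the removals differ too. Because the affected sets are not named, the reader also cannot tell from SAP 3.10 alone which analyses these exclusions touch.

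**Working it through.** No arithmetic applies. The check sets the rules side by side and runs typical patients through them.

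**The rules**

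| Event | Protocol consequence | SAP 3.10 deviation if |
|---|---|---|
| Two missed doses | Stop investigational treatment (5.5.5, 5.5.9) | Patient not discontinued from the study |
| Prohibited medication | Stop investigational treatment (Table 5-1, 5.5.9) | Patient not discontinued from the study |

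**Patients run through the terms as worded**

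| Patient | Handled as the protocol requires? | Meets the SAP term? |
|---|---|---|
| A. Misses two infusions, treatment stopped, attends both remaining visits | Yes | Yes |
| B. Misses two infusions, infusions continue | No | Yes |
| C. Misses two infusions, leaves the study at once | Treatment has stopped; the follow-up visits are not made | No |
| D. Takes a prohibited drug after the last infusion, stays in follow-up | No treatment left to stop | Yes |

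A and B carry the same flag, so the term cannot separate correct from incorrect handling. A and C had the same event, and only A is flagged; the difference is that A stayed. D arises because Table 5-1 applies until Week 48 whereas the last infusion is at Week 20 (Protocol 3.1). For D the protocol's action has nothing to act on, and the only way to avoid the SAP term is to leave the study.

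**Is it only loose wording?** The missed-infusion category also contains the terms on withdrawn consent and on unblinding, and both refer to treatment. The protocol glossary defines treatment discontinuation and premature patient discontinuation separately. SAP 3.10 says that deviations may be identified programmatically by code, so the literal wording can decide who is flagged.

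**Which sets are affected?**
- SAP 2.7 defines the FAS and the safety set by randomisation and infusion received, with no deviation-based exclusion. PP and modified PP are the sets defined by major deviations.
- The next list in SAP 3.10 names the PP set explicitly; the list holding these two terms does not. Receipt of a wrong dose or strength appears in both lists, so their scopes are not cleanly separated.
- The set-by-set handling at the end of SAP 3.10 (safety as treated, FAS as randomised, PP excluded) covers assigned-versus-actual treatment discrepancies only.
- SAP 2.8.1 plans to tabulate reasons for exclusion from the safety set and the FAS as well as from PP.

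The definitions point to the PP sets, but the text of 3.10 does not say so.

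**How many patients?** Neither document gives an expected number with two missed infusions or with prohibited-drug use, so the number cannot be derived.

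**The case against.** The strongest reply has four parts.

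1. *Exclusion is not automatic.* SAP 3.10 requires potential deviations to be confirmed, makes exclusion a decision of the sponsor clinical team, and leaves the coding to a separate edit specification that is not in these documents. This stands, and a correct edit specification may already limit the damage. It does not repair a written term that conflicts with the protocol.

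2. *Such patients do not belong in a PP set anyway.* The protocol itself calls two missed doses a departure from the dose regimen, and PP sets select on such events by design. Protocol 9.2 also requires PP patients to complete the study, which section 5.5.13 sets at 48 weeks; a patient who stops treatment early and ends 4 weeks after the end-of-treatment visit would not. The principle stands. But SAP 2.7 does not carry the completion condition, and the SAP criterion is not the event. It is staying in the study after the event, and it leaves patient C unflagged.

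3. *The terminology is loose throughout.* SAP 3.5.1 also describes patients as discontinuing from the study when they then attend an end-of-treatment visit. That makes a drafting slip plausible, which is a reason to correct it.

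4. *The primary analysis is untouched.* It uses the FAS, and PP is supportive. This stands and limits the weight of the point.

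Three stronger readings are tempting and are not supported. A reader might infer that the terms fail to catch treatment continued against the protocol; they do catch it, since patient B is still in the study. A reader might infer that patients are lost from the FAS or the safety set; nothing in SAP 2.7 provides for that. A reader might take planned non-completion of treatment as an upper bound: Protocol section 4 expects about 200 of about 245 to complete, so 245 − 200 = 45, and 45/245 = 18%. That figure covers every reason for not completing, and it omits treatment completers who take a prohibited drug during follow-up, so it neither estimates nor bounds the number.

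**Conclusion.** The two terms conflict with the protocol and are over-inclusive. Applied as written, they make the deviation summary misleading and distort the PP and modified PP sets, and hence the PP confirmation of the primary result. The size is unknown and cannot be obtained from the documents. The conclusion assumes that the terms, or codes built on them, are applied literally; confirmation by the sponsor clinical team could reduce the effect. Whether the FAS or the safety set could be touched is an unresolved ambiguity, with the definitions in SAP 2.7 pointing against it. The point merits correction before unblinding but does not threaten the primary FAS analysis. It takes no position on which clinical rule is right.

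**What to change.** Before unblinding:

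- Reconcile the two terms in SAP 3.10, and the matching entries in the deviation edit specifications, with Protocol 5.5.5, 5.5.8 (Table 5-1) and 5.5.9, so that a patient managed as the protocol requires can be told apart from one who was not.
- State how prohibited medication taken after the last infusion is classified.
- State that these deviations affect the PP and modified PP sets only, and that the FAS and the safety set remain as defined in SAP 2.7.
- If the intention is to remove every patient with two missed infusions or prohibited medication from PP, make that event the criterion, whether or not the patient stayed in the study.

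The cost is wording in the SAP and the edit specifications, plus a blinded recheck of deviations already flagged. No new data are needed.

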3.11 Statistical methodology and assumptions

3.11.1 Mixed Model Repeated Measures (MMRM)

The following MMRM model will be used for analysis of change from Baseline in total LBM (kg):

Change from Baseline in total LBM = intercept + treatment group + Baseline total LBM + region + treatment date + visit + treatment group*visit + Baseline total LBM*visit + region*visit + treatment date*visit error.

An unstructured covariance matrix will be used for the Week 24 analyses The Kenward-Roger approximation will be used to estimate denominator degrees of freedom.

Residual/restricted maximum likelihood (REML) method will be used to estimate parameters.

The SAS[®] procedure MIXED will be used with the following code:

```
proc mixed data=.... order=internal;  
class sidla trtn vis_1n region trtdt;  
model chg_1n = trtn vis_1n bsval region trtdt trtn*vis_1n region*vis_1n  
trtdt*vis_1n bsval*vis_1n / ddfm=kr;  
repeated vis_1n / patient=sidla type=UN;  
lsmeans trtn*vis_1n/ diff cl;  
run;
```

where chg_1n = change from Baseline in total LBM (kg)

trtn = treatment group

bsval = Baseline LBM value

region = region (Japan/Non-Japan)

trtdt = treatment date (early/late)

vis_1n = visit (here: vis_1n = 1 implies Baseline, vis_1n = 12 implies Visit at Week 12, vis_1n = 24 implies Visit at Week 24 [windowed])

The LSM, standard error and associated 95% confidence interval for treatment effects will be presented. The LSM, standard error, associated two-sided 95% CI, and two-sided p-value for the treatment differences “BYM338 700 mg – Placebo” and “BYM338 210 mg – Placebo” will be presented. The Holm-Bonferroni method will be used to adjust the Type I error for the two comparisons (bimagrumab 700 mg versus placebo and bimagrumab 210 mg versus placebo) treatment group at Week 24. No control for multiplicity will be made at Week 12. The default options in the SAS[®] procedure MIXED will be used otherwise i.e. the LSM will use the mean value of the covariate(s). The L matrix coefficients for the LSMEANS are as follows: Baseline LBM: 0.4644kg; Visit (either 12 or 24 weeks): 1; Geographic Region (either Japan or Non-Japan): Non-Japan; Treatment Date (either Early or Late): Late.

Other variables (derived gait speed [m/sec], total SPPB, [redacted] [g/cm²], [hip]) will be analyzed with a similar MMRM model as used for change from Baseline in total LBM (kg), including appropriate windowed post-baseline visits (repeated measures) and additional covariates, as specified in [Section 2.10.2.3](#) (Statistical model, hypothesis, and method of analysis [secondary]). If the primary efficacy endpoint is significant, the testing strategy, as described in [Section 2.10.2.3](#) (Statistical model, hypothesis, and method of analysis [secondary]), will be used to control for the fact that we have two secondary endpoints:

If both doses (bimagrumab 700 mg and bimagrumab 210 mg) are statistically significantly different from placebo at $\alpha = 0.05$ two-sided for the primary endpoint, then a step down approach will be applied for both derived gait speed (m/sec) and total SPPB score at Week 24 using the same linear MMRM.

For derived gait speed (m/sec), the L matrix coefficients for the LSMEANS are as follows: Baseline derived gait speed: 0.4682 m/sec; Visit (either 12, 24, 36 or 48 weeks): 1; Geographic Region (either Japan or Non-Japan): Non-Japan; Treatment date (either Early or Late): Late; Fracture fixation type (Arthroplasty or Internal): Internal; History of falls (12 months): (either Yes or No): No; Use of mobility aids prior to hip fracture (3 months) (Yes or No): No.

For total SPPB score, the L matrix coefficients for the LSMEANS are as follows: Baseline total SPPB score: 5.5804; Visit (either 12, 24, 36 or 48 weeks): 1; Geographic Region (either Japan or Non-Japan): Non-Japan; Treatment date (either Early or Late): Late; Fracture fixation type (Arthroplasty or Internal): Internal; History of falls (12 months): (either Yes or No): No; Use of mobility aids prior to hip fracture (3 months) (Yes or No): No.

Total LBM (kg) data will be transformed with natural logarithm before analysis. The residuals from the MMRM analyses, are to be visually checked for normality and homogeneity of variance. For derived gait speed (m/sec) and total SPPB score, normality is to be examined by normal probability plots, while homogeneity of variance is to be assessed by plotting the residuals against the predicted values for the model and via Levene's test using the following example SAS[®] code:

```
proc glm data = ....;
class trt;
model y = trt;
means trt / hovtest=levене;
run;
```

If the data is not normally distributed, this data will also be transformed with natural logarithm before analysis. The antilog of the point estimate and associated 95% confidence interval of the active treatment versus placebo treatment difference will be computed prior to presentation.

